### 3.6.2. Outliers

Outliers will be identified during data management and data analysis process, but no sensitivity analyses will be done to evaluate the impact of outliers on efficacy or safety outcomes. All data will be included in the data analysis.

## 3.7. Visit Windows

### 3.7.1. Definition of Study Day 1, Last Dosing Date, and Baseline

The **first dose date of individual study drug** will be calculated separately for each study drug (ie, SOF or RBV). **Study Day 1** is defined as the **first dose date of any study drug**, which is the minimum of the first dose dates of individual study drugs.

The **date of last dose of individual study drug** will be calculated separately for each study drug. The date of last dose for an individual study drug will be the end date on study drug administration CRF for the record where the “subject permanently discontinued” flag is ‘Yes’. The **last dose date of any study drug** will be defined as the maximum of the last dosing dates of individual study drugs.

If there are subjects for whom the date of last study drug is unknown due to the reason that the subject was lost to follow-up, the date of last dose will be estimated using the maximum of nonmissing study drug start or stop dates and on-treatment visit dates and laboratory collection dates (Post-treatment visits and unscheduled visits are not included).

In general, the **baseline value** will be the last nonmissing value on or prior to the first dose date of study drug. If multiple measurements occur on the same day, the last non-missing value prior to the time of first dose of study drug will be considered as the baseline value. If these multiple measurements occur at the same time or time is not available, the average of these measurements (for continuous data) or the worst among these measurements (for categorical data) will be considered as baseline value.

### 3.7.2. Analysis Windows

Subject visits might not occur on protocol-specified days. Therefore, for the purposes of analysis, visit windows will be utilized when a single value at a visit is required for analysis.

Visit windows are defined for HCV RNA data, safety laboratory data (which includes HIV RNA and CD4 counts). No analysis windows will be defined for health related quality of life data and pregnancy test.

All available HCV RNA data will be included in efficacy analysis, unless a subject starts alternative HCV medication. HCV RNA data collected after starting alternative HCV medication will be excluded. Imputation for missing HCV RNA values are described in Section 3.6.1. For safety data, subjects who are permanently discontinued from study drug will be included in safety analyses to the **last dose date of any study drug** + 30 days, unless otherwise specified. For interim DMC analyses, subjects still on study drug will have all available data included in the interim snapshot database included in analysis.

HCV RNA, vital signs, and safety laboratory test data collected up to the **last dose date of any study drug** + 2 days are considered to be on-treatment data and HCV RNA, vital signs and safety laboratory data collected after the **last dose date of any study drug** + 2 days are considered posttreatment data. On-treatment and posttreatment data will follow 2 different sets of visit windows.

Visit windows will be calculated from **Study Day 1** (ie, Study Day = collection date minus date **Study Day 1**; +1 if result is  $\geq 0$ ) for HCV RNA, vital signs and other safety laboratory data as shown in Table 2.

Table 2. On-Treatment Visit Windowsa

Visit ID	On-Treatment Visit Windows for Group 1 (GT2/3 TN Subjects, SOF+RBV 12 weeks)	On-Treatment Visit Windows for Group 2 and 3 (GT2/3 TE and GT1 TN Subjects, SOF+RBV 24 weeks)
Baseline	Study Day ≤ 1	Study Day ≤ 1
Week 1	2 ≤ Study Day ≤ 11	2 ≤ Study Day ≤ 11
Week 2	12 ≤ Study Day ≤ 21	12 ≤ Study Day ≤ 21
Week 4	22 ≤ Study Day ≤ 35	22 ≤ Study Day ≤ 35
Week 6	36 ≤ Study Day ≤ 49	36 ≤ Study Day ≤ 49
Week 8	50 ≤ Study Day ≤ 63	50 ≤ Study Day ≤ 63
Week 10	64 ≤ Study Day ≤ 77	64 ≤ Study Day ≤ 77
Week 12	78 ≤ Study Day ≤ 98	78 ≤ Study Day ≤ 98
Week 16	NA	99 ≤ Study Day ≤ 126
Week 20	NA	127 ≤ Study Day ≤ 154
Week 24	NA	155 ≤ Study Day ≤ 182

a. This table will apply to all HCV RNA, vital signs and safety labs including HIV RNA and CD4 counts.

HCV RNA, vital sign, and safety laboratory data collected after the *last dose date of any study drug* + 2 days will be assigned to the posttreatment FU visit windows. Windows will be calculated from the *last dose date of any study drug* (ie, FU Day = collection date minus the *last dose date of any study drug*) as shown in Table 3.

Table 3. Post-treatment Visit Windows for Selected Tests

Off-Treatment FU Visit ID	Post-treatment Visit Windows for HCV RNA a (Days from Last Dose Date)	Post-treatment Visit Windows for HIV RNA and CD4 Count b (Days from Last Dose Date)	Other Safety Labs b (Days from Last Dose Date)
FU-4	21 ≤ FU Day ≤ 69	3 ≤ FU Day ≤ 56	3 ≤ FU Day ≤ 30
FU-12	70 ≤ FU Day ≤ 146	57 ≤ FU Day ≤ 126	N/A
FU-24	147 ≤ FU Day ≤ 190	127 ≤ FU Day ≤ 190	N/A

a SVR follow-up visit window (lower bound) must occur within 7, 14, and 21 days of target for SVR4, SVR12, and SVR24, respectively.

b Vital signs and safety labs (except HIV RNA and CD4 counts) will only be summarized for the 4-week follow up visit (up to 30 days post last dose)

c HIV RNA and CD4 counts will be summarized through 24-week follow up visit.

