## 2. OBJECTIVES

The primary objectives of this study are:

- To determine the efficacy of treatment with GS-7977 + RBV as measured by the proportion of subjects with sustained viral response 12 weeks after discontinuation of therapy (SVR12)
- To evaluate the safety and tolerability of GS-7977 + RBV as assessed by review of the accumulated safety data, including HIV-RNA and CD4 T-cell percent

The secondary objectives of this study are as follows:

- To determine the proportion of subjects who attain SVR at 4 and 24 weeks after discontinuation of therapy (SVR4 and SVR24)
- To evaluate the kinetics of circulating HCV RNA during treatment and after treatment discontinuation
- To evaluate the emergence of viral resistance to GS-7977 during treatment and after treatment discontinuation

The exploratory objectives of this study are:

- To identify or validate genetic markers that may predict the natural history of disease, response to therapy and/or the tolerability of medical therapies through genetic discovery research (e.g., pharmacogenomics), in subjects who provide their separate and specific consent
- To assess the effect of treatment on health related quality of life

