#### **3.2. Visit Schedule**

All subjects will complete screening, on-treatment and post-treatment assessments. Screening assessments will be completed within 28 days of the Baseline/Day 1 visit. All subjects will complete a 4-Week Post-Treatment visit regardless of treatment duration. Subjects with HCV RNA < LLOQ at the 4-Week Post-Treatment Visit will complete 12-Week and 24-Week Post-Treatment visits unless confirmed viral relapse occurs.

The assessments performed at each visit are described in Section 6.

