**6.3. Post-Treatment Assessments**

**6.3.1. 4-Week Post-Treatment Visit ( $\pm$  3 days)**

- Obtain vital signs
- Assessment of AEs and concomitant medications

- Obtain blood samples for:
  - Hematology
  - Chemistry
  - HCV RNA
  - HIV RNA
  - CD4 T-lymphocyte Absolute Count and %
  - Viral sequencing (archive)
- Urine  $\beta$ -hCG pregnancy test for females of childbearing potential only
- Pregnancy prevention counseling
- Subject completes quality of life surveys

Female subjects of childbearing potential should be provided with Urine Pregnancy Test-Kits, instructed on their use and requested to continue to self-monitor for pregnancy for 6-months after their last dose of RBV. If required by regulations, additional pregnancy tests beyond 6 months may be added. The subject should be contacted every 4 weeks and asked to report results of the urine pregnancy tests. If a positive urine pregnancy test is reported, the subject should return to the clinic for a serum pregnancy test.

Subjects with HCV RNA < LLOQ at the 4-Week Post-Treatment Visit will attend the 12-Week Post-Treatment Visit.

Subjects with a confirmed HCV RNA  $\geq$  LLOQ at the Post-Treatment Week 4 Visit will be offered participation in the Sequence Registry Study.

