## **7.2. Laboratory Evaluations**

Summaries of laboratory data will be provided for the safety analysis set and will include data collected up to last dose of any study drug plus 30 days (except HIV RNA and CD4 data, which is through the end of the study) for subjects who have stopped all study drugs and all available data at the time of the database snapshot for subjects who are ongoing at the time of this analysis. Analysis will be based on values reported in conventional units. Laboratory results cancelled by the central laboratory will not be included in analysis.

No inferential statistics will be generated.

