### **7.2.1. Summaries of Numeric Laboratory Results**

Descriptive statistics (sample size, mean, standard deviation, median, Q1, Q3, minimum and maximum) will be provided by treatment group for ALT, AST, total bilirubin, alkaline phosphatase, white blood cell (WBC) counts, neutrophils, lymphocytes, hemoglobin, platelets, reticulocytes, PT, and INR, and CD4 counts (absolute and %) as follows:

- Baseline values
- Values at each post-baseline analysis window
- Change from baseline at each post-baseline analysis window

The mean, median, Q1, Q3, minimum and maximum will be displayed to reported number of digits, standard deviation to reported number of digits +1 for visits up to end of treatment.

Median (Q1, Q3) of the absolute values for these laboratory parameters will be plotted by treatment group and visit. In the case of multiple values in an analysis window, data will be selected for analysis as described in Section 3.6.3.

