### **7.5. Other Safety Measures**

A data listing for cirrhosis determination will be provided for all subjects at screening.

A data listing will be provided for subjects who become pregnant during the study.

The shift in toxicity grade for total bilirubin from baseline to maximal grade at post-baseline will be summarized by Atazanavir (ATV) status at enrollment for each treatment group.

In addition, the following analysis will be conducted for subjects on ARV at baseline and for subjects not on ARV at baseline respectively:

- SVR12 endpoint analysis with the virologic outcome
- Summary of absolute value and change from baseline by visit for the following laboratory analytes: CD4 counts (absolute and %).

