18.11	CD4 Counts ( $\text{cells}/\text{mm}^3$ ) and Change from Baseline by Visit	Safety Analysis Set
18.12	CD4 Counts (%) and Change from Baseline by Visit	Safety Analysis Set
19.1	Treatment-Emergent Graded Laboratory Abnormalities	Safety Analysis Set
19.2	Treatment-Emergent Grade 3 or 4 Laboratory Abnormalities	Safety Analysis Set
20	Shift in Toxicity Grade for Total Bilirubin from Baseline to Maximal Post-baseline Grade by Atazanavir Status at Enrollment	Safety Analysis Set
21	Proportion of Subjects with HIV Virologic Rebound for Subjects Who Were on ARV Treatment at Enrollment	Safety Analysis Set
22.1	HCV Virologic Outcome for Subjects on ARV at Baseline	Full Analysis Set
22.2	HCV Virologic Outcome for Subjects Not on ARV at Baseline	Full Analysis Set
23.1	CD4 Counts ( $\text{cells}/\text{mm}^3$ ) and Change from Baseline by Visit for Subjects on ARV at Baseline	Safety Analysis Set
23.2	CD4 Counts ( $\text{cells}/\text{mm}^3$ ) and Change from Baseline by Visit for Subjects Not on ARV at Baseline	Safety Analysis Set
23.3	CD4 Counts (%) and Change from Baseline by Visit for Subjects on ARV at Baseline	Safety Analysis Set
23.4	CD4 Counts (%) and Change from Baseline by Visit for Subjects Not on ARV at Baseline	Safety Analysis Set

Figure Number	Title	Analysis Set
1.1	Median (Q1, Q3) ALT (U/L) by Visit	Safety Analysis Set
1.2	Median (Q1, Q3) AST (U/L) by Visit	Safety Analysis Set
1.3	Median (Q1, Q3) Total Bilirubin (mg/dL) by Visit	Safety Analysis Set
1.4	Median (Q1, Q3) Alkaline Phosphatase (U/L) by Visit	Safety Analysis Set
1.5	Median (Q1, Q3) WBC ( $\times 10^3/\mu\text{L}$ ) by Visit	Safety Analysis Set
1.6	Median (Q1, Q3) Neutrophils ( $\times 10^3/\mu\text{L}$ ) by Visit	Safety Analysis Set
1.7	Median (Q1, Q3) Lymphocytes ( $\times 10^3/\mu\text{L}$ ) by Visit	Safety Analysis Set
1.8	Median (Q1, Q3) Hemoglobin (g/dL) by Visit	Safety Analysis Set
1.9	Median (Q1, Q3) Platelets ( $\times 10^3/\mu\text{L}$ ) by Visit	Safety Analysis Set
1.10	Median (Q1, Q3) Reticulocytes ( $\times 10^3/\mu\text{L}$ ) by Visit	Safety Analysis Set
1.11	Median (Q1, Q3) CD4 Counts (cells/mm  ) by Visit	Safety Analysis Set
1.12	Median (Q1, Q3) CD4 Counts (%) by Visit	Safety Analysis Set
2.1	Median (Q1, Q3) CD4 Counts (cells/mm  ) by Visit by ARV at Baseline	Safety Analysis Set
2.2	Median (Q1, Q3) CD4 Counts (%) by Visit by ARV at Baseline	Safety Analysis Set
3.1	Forest Plot of SVR4 by Subgroup	Full Analysis Swet

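### The FU-12 and FU-24 points of the by-visit CD4 displays describe HCV responders only, but appear unlabelled on the same axis as all treated subjects

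*Combined protocol and SAP*

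**What the plan says.** **The analysis.** SAP 3.7.2, Table 3 footnote c: "HIV RNA and CD4 counts will be summarized through 24-week follow up visit". SAP 7.2 cuts other laboratory data at 30 days after the last dose, "except HIV RNA and CD4 data, which is through the end of the study". SAP 7.2.1 asks for descriptive statistics by treatment group, including "Change from baseline at each post-baseline analysis window", and for plots of the median (Q1, Q3) of absolute values by visit. SAP 7.5 repeats the CD4 summaries by ARV status at baseline. Appendix 1 lists the outputs: Tables 18.11 and 18.12 (the latter "CD4 Counts (%) and Change from Baseline by Visit"), Tables 23.1 to 23.4, and Figures 1.11, 1.12, 2.1 and 2.2. All use the Safety Analysis Set, which SAP 3.1.2 defines as everyone enrolled and dosed. SAP 3.6.1 does not impute missing safety data. No CD4 output is split or labelled by HCV outcome. The planned HIV RNA outputs are a rebound proportion and listings, so the by-visit question concerns CD4.

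**The visits.** Protocol 3.2: "Subjects with HCV RNA < LLOQ at the 4-Week Post-Treatment Visit will complete 12-Week and 24-Week Post-Treatment visits unless confirmed viral relapse occurs". Protocol 6.3.1 says that subjects below LLOQ "at the 4-Week Post-Treatment Visit will attend the 12-Week Post-Treatment Visit". Protocol 6.3.2 adds a second gate: Week 24 is for those below LLOQ at Week 12. SAP 1.2.1 restates the first gate. Subjects with confirmed HCV RNA at or above LLOQ are offered a separate registry protocol.

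**The objective.** Protocol 2 describes the safety data under the primary safety objective as "including HIV-RNA and CD4 T-cell percent".

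**The concern.** Up to FU-4, every treated subject is scheduled for a CD4 measurement. From FU-12 on, only HCV responders are, and FU-24 is narrower still. FU-12 holds subjects below LLOQ at Week 4, including late relapsers first detected at FU-12. FU-24 holds only those also below LLOQ at Week 12. The displays put all of these on one visit axis with nothing to mark the change.

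A step between FU-4 and FU-12, or between FU-12 and FU-24, can therefore come from who is measured and not from a change within subjects. That stretch is where a reader looks for CD4 recovery after SOF+RBV. The plots of absolute CD4 are most exposed, because a baseline CD4 difference between responders and failures is enough to move the line. The change-from-baseline rows avoid that part, since each subject is compared with himself or herself, but their late rows still describe responders only.

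**Working it through.** **Inputs.** Protocol 9.8 and SAP 1.3 give planned sizes of about 55, 55 and 115 (225 in all; elsewhere the plan rounds to 230) and expected SVR12 of 62%, 40% and 65% for Groups 1, 2 and 3. No document states how many subjects the FU-12 or FU-24 CD4 rows will hold.

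**The plan's own figures.** Half-width = 1.96 × √(p(1−p)/N):

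- Group 1: 1.96 × √(0.62 × 0.38/55) = 12.83% (stated 12.8%)
- Group 2: 1.96 × √(0.40 × 0.60/55) = 12.95% (stated 12.9%)
- Group 3: 1.96 × √(0.65 × 0.35/115) = 8.72% (stated 8.7%)

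All three agree to within 0.1 point.

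**FU-24, complete follow-up.** The share scheduled is about the SVR12 rate p, so the share absent by design is 1 − p:

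- Group 1: 0.38 × 55 = 20.9 absent, about 34 of 55 left
- Group 2: 0.60 × 55 = 33.0 absent, 22 of 55 left
- Group 3: 0.35 × 115 = 40.3 absent, about 75 of 115 left
- Total: 94.2 of 225 absent (42%), about 131 left

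**FU-12.** The gate is SVR4, so the share scheduled is p divided by the SVR12:SVR4 ratio. Protocol Table 1-5 gives 21/22 = 0.95 (genotype 1 naive) and 17/19 = 0.89 (genotype 2/3 experienced); 1.00 is the limit with no late relapse. Over 0.89 to 1.00:

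- Group 1: 0.62/0.895 = 69% to 62% seen, so 31-38% absent
- Group 2: 0.40/0.895 = 45% to 40% seen, so 55-60% absent
- Group 3: 0.65/0.895 = 73% to 65% seen, so 27-35% absent

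**Effect on a mean.** The all-treated mean is p × (responder mean) + (1 − p) × (failure mean). A row holding responders only therefore differs from it by (1 − p) × D, where D is the responder-minus-failure difference in CD4. The documents do not give D. As an assumption, in cells/mm3:

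| D | Group 1 | Group 2 | Group 3 |
|---|---|---|---|
| 0 | 0 | 0 | 0 |
| 25 | 9.5 | 15 | 8.8 |
| 50 | 19 | 30 | 17.5 |
| 100 | 38 | 60 | 35 |

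A negative D reverses the sign. At 80% or 90% SVR12 the shift is 0.2 × D or 0.1 × D. The formula is for means; the figures plot medians, so it is only indicative there.

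**The data cut.** SAP 2.1 sets the last FU-12 visit for Groups 1 and 3 at about 9 September 2013 and database finalization at about 30 September. A subject whose FU-12 (day 84) falls on 9 September took the last dose on 17 June and is at day 105 on 30 September. The FU-24 window for CD4 opens at day 127. FU-24 will thus also lack recently treated subjects. Group 2 does not trigger the cut and may be only partly followed.

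**The case against.** The strongest reply is that these displays are descriptive and already show much of what is needed. The tables report sample size at each window, change is within subject, SAP 7.2 rules out inferential statistics, and Listings 20, 7.1 and 7.2 give CD4 and HCV RNA by subject. This largely stands, and it confines the problem to the plots and to the labelling of late rows. It does not remove it: a falling n does not say why subjects left, and no n is specified for the plots.

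CD4 is also less central than Protocol 2 alone suggests. That section names CD4 percent. The synopsis, Protocol 9.1.1 and SAP 1.1.1 state the objective without CD4, and the primary safety endpoint is an adverse event leading to permanent discontinuation. This stands and limits the weight of the point.

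The planning rates may also prove wrong. Protocol 1.6 cites SVR4 of 53% to 100% in treatment-naive genotype 1, which would put the Group 3 loss at FU-12 anywhere from 0 to 47%. That is fair, and higher response shrinks the effect.

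SAP 7.2.1 mentions visits up to end of treatment, which might suggest that the CD4 summaries stop there. That phrase sits in a sentence on displayed digits, while SAP 3.7.2, 7 and 7.2 each carry CD4 further.

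Finally, a footnote and n would answer most of this. They are part of the fix, but they do not let a reader separate a change in subjects from a change in CD4. Earlier values for the same subjects do.

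**Conclusion.** The point holds as a modest, cheap improvement to descriptive safety displays. Both gates are explicit, and nothing in the SAP labels the late CD4 rows as HCV responders. With complete follow-up at the planning rates, 38%, 60% and 35% of the three groups (42% overall) are absent by design at FU-24, and about 31-38%, 55-60% and 27-35% at FU-12. These figures assume that attendance follows the gates and that the SVR12:SVR4 ratio is 0.89 to 1.00. They do not predict row sizes at the September 2013 cut, where administrative incompleteness comes on top.

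A reader might infer two stronger things. One is that the CD4 results will be off by tens of cells, or will show a false recovery or loss. The documents do not support that: they give no CD4 difference between responders and failures, D may be zero, and its sign is unknown. The other is that the FU-24 losses apply equally to the FU-4 to FU-12 step. They are only the upper end there, because subjects who relapse after Week 4 still attend FU-12. What is established is a change in who is measured, not a bias of known size.

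**What to change.** In SAP 7.2.1 and 7.5, for Tables 18.11, 18.12 and 23.1 to 23.4 and Figures 1.11, 1.12, 2.1 and 2.2:

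- Make FU-4 the last visit of the all-treated CD4 trend.
- Show FU-12 and FU-24 in a separate panel labelled as HCV responders. For each late visit, show baseline, end-of-treatment and FU-4 values for the same subjects who have a CD4 value at that visit. Defining the comparison by an observed value at each late visit handles the second gate and the data cut as well as the first gate.
- Footnote both HCV RNA gates and the data cut.
- Print n under each point of the plots.
- Keep all late values in the listings.

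The cost is SAP wording, changed shells and one extra panel per table or figure. No visit or sample is added and no data are discarded.

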### **3.7.3. Selection of Data in the Event of Multiple Records in a Window**

Depending on the statistical analysis method, single values may be required for each analysis window. For example, change from baseline by visit usually requires a single value, whereas a time-to-event analysis would not require 1 value per analysis window. When a single value is needed, the following rules will be used:

- Select the record closest to the nominal day (ie, visit weeks x 7 days) for that visit except for HCV RNA posttreatment follow-up visits, for which the latest record in the analysis window should be selected.
- If there are 2 visits equidistant from the nominal day within the analysis window, take the latest.
- If there is more than 1 record on the selected day, take the average (for continuous data) or the worst (for categorical data). If there are 2 values on the same day, the second may be a retest because there was a problem with the first test (eg, specimen hemolyzed). In cases where the first test is cancelled, the retest value should be used.

## **4. SUBJECT DISPOSITION**

### **4.1. Disposition of Subjects**

A summary of subject disposition will be provided by treatment group and overall. This summary will present the number of subjects who were screened, enrolled, enrolled and treated (ie, safety analysis set), and FAS and the number and percentage of subjects meeting the following criteria:

- Completed study treatment
- Did not complete study treatment (with summary of reasons for not completing the study treatment period)
- On study treatment (if applicable)
- Completed the study
- Did not complete the study (with summary of reasons for not completing the study)
- On study

The denominator for the percentages of subjects in each category will be the number of subjects in the safety analysis set.

No inferential statistics will be generated.

A data listing of date of informed consent, first dose date, last dose date of any study drug (study day), completed study treatment (yes/no), completed study (yes/no) and reasons for premature study treatment/study discontinuation will be provided. The last available observed nonmissing HCV RNA value prior to discontinuation and for up to 2 days after last dose will be included in this listing.

